4.0 Enrollment/Randomization

We will conduct a single center, randomized, double-blind, double-dummy, parallel design trial comparing oral metolazone, intravenous chlorothiazide, and oral tolvaptan in combination with loop diuretics in patients hospitalized for hypervolemic acute heart failure. The duration of the study will be 48 hours from the first dose of the study thiazide or tolvaptan medication. Vanderbilt University Medical center will be the study site. IRB approval will be obtained from the Vanderbilt University Medical Center IRB.

All patients will provide informed consent prior to enrollment. After enrollment, all patients will be randomized in a 1:1:1 fashion at VUMC using a random number table in the investigational drug services pharmacy. The investigational pharmacists will perform randomization, and investigators will be blinded to the treatment arm.

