7.0 Reporting of Adverse Events or Unanticipated Problems involving Risk to Participants or Others

A **Serious Adverse Event (SAE)** is an adverse event that:

- Results in death
- Is life-threatening
- Requires prolongation of hospitalization which is not specifically required by the protocol nor is it elective
- Results in permanent impairment of a body function or permanent damage to a body structure
- Requires medical or surgical intervention to preclude permanent impairment of a body function or permanent damage to a body structure

Additionally, important medical events that may not result in death, be life-threatening, or prolong hospitalization may be considered SAEs when they jeopardize the patient or require medical or surgical intervention to prevent one of the serious outcomes listed above. Example of such medical events include: allergic bronchospasm requiring intensive treatment in an emergency room or at home, blood dyscrasias or convulsions that do not result in prolonged hospitalization, or the development of drug dependency or drug abuse. Medical and scientific judgment must be exercised when classifying events as serious.

The determination of adverse event severity rests on medical judgment of a medically qualified investigator. The severity of SAEs will be graded using the following definitions:

- **Mild:** awareness of sign, symptom, or event, but easily tolerated;
- **Moderate:** discomfort enough to cause interference with usual activity and may warrant intervention;
- **Severe:** incapacitating with inability to do usual activities or significantly affects clinical status, and warrants intervention.

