7.2 Reporting of SAE

All serious adverse events occurring from randomization through the 30 day follow-up period will be collected. The Site Investigator is responsible for monitoring the safety of patients enrolled into the study. The following adverse events are anticipated, disease related-events in patients with decompensated heart failure however they should still be reported on the Serious Adverse Event form in the REDCAP Database (some may require reporting as study endpoints):

- New Atrial Arrhythmia: A “new” diagnosis of atrial arrhythmia (includes atrial fibrillation, atrial flutter, ectopic atrial tachycardia) lasting > 30 seconds OR any atrial arrhythmia which causes hemodynamic instability (MAP < 60 and requiring intervention)
- New Ventricular Arrhythmia: Ventricular tachycardia lasting longer than 30 seconds, or frequent non-sustained VT causing hemodynamic instability with MAP < 60 mmHg requiring intervention or > 1 intra-cardiac defibrillation or external cardiac defibrillation shock or ventricular fibrillation requiring defibrillation
- Hypotension: SBP < 85 for 2 repeated measurements within 30 minutes or lasting at least 30 minutes or symptomatic hypotension necessitating clinical intervention (defined as vasopressor support, intravenous fluid boluses, or initiation of inotropes)
- Myocardial infarction: a cardiac event including an elevation in troponin above baseline with or without ECG changes that is judged to be a myocardial infarction by the treating attending cardiologist
- Cardiac arrest: any ventricular arrhythmic or pulseless electrical event that requires immediate life-sustaining medical therapies
- Acute renal failure: A rise in serum creatinine of 1 mg/dl or more from the baseline serum creatinine in the 48 hour treatment period
- Acute renal failure requiring dialysis: an acute renal failure event that began during the 48 hour study period and necessitates new hemodialysis during the hospitalization

- Worsening heart failure: the need for rescue therapy (additional open label loop diuretic, spironolactone doses >75mg/day, eplerenone > 75mg/day, non-study thiazides (at a dose of metolazone 2.5mg or greater equivalence), systemic acetazolamide (for diuretic indication), triamterene, amiloride, ultrafiltration, hemodialysis, or mechanical circulatory or respiratory support) in the 48 hour treatment period
- Death
- Metabolic SAE (during 48 hour treatment period):
 - Severe Hypokalemia: Serum potassium value < 3.0mEq/L

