 - Severe Hyponatremia: Serum sodium value < 130mEq/L and a decrease of 5mEq/L or more from enrollment serum sodium
 - Overcorrection of serum sodium: increase in serum sodium from baseline by ≥ 12 mEq/L in 24 hours, increase in >8mEq/L in 12 hours, or receipt of intravenous fluids because of symptoms of overcorrection of serum sodium regardless of the numerical rise
 - Hyperkalemia: serum potassium value > 5.5mEq/L
 - Gout: acute gout attack requiring treatment with an anti-inflammatory agent

All serious adverse events must be recorded in the Serious Adverse Event Record of the patient's REDCAP database. All serious adverse events should be monitored until stabilization or resolution.

Reporting to Local IRB. Investigators are also responsible for promptly reporting unexpected adverse events (serious and non serious) to their reviewing IRB in accordance with local requirements. The Vanderbilt investigational site will report DSM reports to the Vanderbilt IRB annually at the time of continuing review at a minimum. If 5 unexpected SAEs occur, the trial will be temporarily halted and the Vanderbilt IRB will be informed. After review, the study will resume if the IRB approves continuation with or without alterations in the study protocol.

Reporting to the Industry Sponsor

The investigator will notify the Sponsor within 24 hours of being notified of any SAE. The investigator will also notify the Sponsor of any pregnancy during the study period within 3 days of being notified. For all non-serious adverse events, the investigator will notify the Sponsor of all events as a line item list at the end of the study.

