Appendix C: 30-Day Follow up Telephone Call Script

The site investigator will perform this phone call at 30 ± 2 days after enrollment.

Hello, my name is Dr. (name) from (Medical Center). I am calling to briefly follow up with you about the research study you participated in during your recent hospitalization for heart failure approximately one month ago. The study compared 3 different types of fluid removal medications in combination with furosemide (Lasix) and was called “Comparison of oral thiazides versus intravenous thiazides versus tolvaptan in combination with loop diuretics for diuretic resistant decompensated heart failure”.

Do you have time now to complete the brief post-study survey that was mentioned to you at the start of the study? It should take no more than 5 minutes of your time. Thank you for your participation.

If subject has deceased since discharge

I am very sorry for your loss. It is important that we ask 3 simple questions to understand this unfortunate event. Could you please tell me:

- Date of death
- Cause of death
- Location of death
 - Out-of-hospital
 - In-hospital
 - Initial reason for hospitalization

If subject is alive

Since your discharge from (Medical Center) on (Discharge Date), have you experienced any of the following events?

1. Admission to any hospital?
 - a. Admission reason:
 - i. Heart failure
 - ii. Heart rhythm issue
 - iii. Low blood pressure
 - iv. Heart attack
 - v. Cardiac arrest
 - vi. Kidney failure
 1. Was dialysis required?
 - vii. Other (free text)
2. Gone to any emergency room?
 - a. Reason for emergency room visit:
 - i. Heart failure
 - ii. Heart rhythm issue

- iii. Low blood pressure
- iv. Heart attack
- v. Cardiac arrest
- vi. Kidney failure
- vii. Other (free text)

- 3. Any other serious health event?
 - a. Document event if so

This ends your participation in this research study. Thank you very much for your participation in this research study and for your time today. Your participation is helping our medical team understand how to treat patients with heart failure better. Do you have any other questions at this time?

Goodbye.

End of Script

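### The SAE definition counts prolonged but not new hospitalization, so a post-discharge readmission as such, notably for heart failure or kidney failure, meets no listed criterion although SAEs are collected to Day 30

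*Combined protocol and SAP*

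**What the plan says.** Section 7.0 defines an SAE by five criteria: death, threat to life, prolonged hospitalization, permanent impairment or damage, and intervention to preclude permanent impairment or damage. The hospitalization criterion is "Requires prolongation of hospitalization which is not specifically required by the protocol nor is it elective". A further clause allows that important medical events "may be considered SAEs when they jeopardize the patient or require medical or surgical intervention to prevent one of the serious outcomes listed above", on medical judgment.

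The collection window is set in section 7.2: "All serious adverse events occurring from randomization through the 30 day follow-up period will be collected". Treatment is much shorter. Section 4.0 says "The duration of the study will be 48 hours from the first dose".

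Section 7.2 also lists anticipated, disease-related events that must still go on the SAE form. Sponsor reporting has two speeds. For SAEs, "The investigator will notify the Sponsor within 24 hours of being notified of any SAE". For non-serious events, "the investigator will notify the Sponsor of all events as a line item list at the end of the study".

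At Day 30 the telephone call (section 5.6 and Appendix C) asks about hospital admissions and emergency-room visits, with reasons. Section 5.6 lists serious adverse events as a separate item of the same call.

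**The concern.** Prolongation presupposes a patient who is already in hospital. Once the patient is discharged, a new admission cannot meet that criterion by happening, and no other criterion names it. The definition is written for the inpatient phase, while the collection window extends past it.

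SAE status drives several duties: severity grading (7.0), causality assessment (7.1), the SAE record and the 24-hour sponsor notice (7.2), and the count of unexpected SAEs that halts the trial (7.2 and 7.3). An event that misses the definition misses all of these. With only a permissive clause to fall back on, two investigators could classify the same readmission differently and both comply with the protocol.

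**Working it through.** The plan states no figure on this point, so the check compares the text of the sections.

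**Step 1. The five criteria against a new admission.** Take a readmission that is not fatal or life-threatening, causes no permanent impairment and needs no intervention to preclude it. Four criteria fail by construction. The fifth, prolongation, does not describe a new admission. None of the five is met.

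**Step 2. The important-medical-event clause.** It could reach such an admission, but it is permissive, rests on judgment and does not mention new hospitalization. It makes classification possible, not required.

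**Step 3. The 7.2 list against the admission reasons in Appendix C.** The script names six reasons, plus a free-text category.

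| Admission reason (Appendix C) | Related entry in 7.2 | Time limit on that entry |
|---|---|---|
| Heart rhythm issue | New atrial or ventricular arrhythmia | None |
| Low blood pressure | Hypotension | None |
| Heart attack | Myocardial infarction | None |
| Cardiac arrest | Cardiac arrest | None |
| Heart failure | Worsening heart failure | 48-hour treatment period |
| Kidney failure | Acute renal failure; the same requiring dialysis | Creatinine rise in the 48-hour period; the dialysis entry needs onset in that period |

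Four of the six correspond to untimed entries and go on the SAE form through Day 30 where their definitions are met. Two do not. The worsening heart failure entry ends with "mechanical circulatory or respiratory support) in the 48 hour treatment period". The metabolic events are limited to the same 48 hours. Admissions in the free-text category have no entry of their own unless they match one of the list's other events.

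**Step 4. Window lengths.** The timed entries cover 48 hours. SAE collection covers about 30 days: 30 × 24 = 720 hours, and 48 / 720 = 1/15. For the rest of the window those entries cannot apply. The documents give no length of stay, so how much of that time falls after discharge is not known.

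**Step 5. What follows for a heart failure or kidney readmission, absent another route.**
- Recorded: yes, with its reason, at the Day 30 call.
- Severity grading and causality assessment: not required, since 7.0 and 7.1 ask for these for SAEs.
- Sponsor: end-of-study line list, not 24 hours from notification.
- Halt: 7.2 and 7.3 count unexpected SAEs, so even a readmission judged unexpected under 7.1 would not be counted.

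**The case against.** The strongest reply is that the gap is narrow and partly covered elsewhere. Much of that is correct.

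- A reader might infer that all readmissions escape SAE reporting. They do not. Arrhythmia, hypotension, myocardial infarction and cardiac arrest are untimed in 7.2, and other readmissions may qualify as fatal, life-threatening or needing intervention to preclude permanent impairment.
- A reader might infer that readmissions are lost or hidden. They are not. The Day 30 call records them. Section 7.2 also requires prompt reporting of unexpected adverse events to the IRB whether or not they are serious, and non-serious events reach the sponsor at the end.
- A reader might infer that a comparison of 30-day SAEs between arms is compromised. Section 5.4 lists no SAE rate or 30-day endpoint, and section 9.3 specifies no such analysis.
- A reader might take the script's closing question, "Any other serious health event", as showing that the protocol already regards admissions as serious. That question follows emergency-room visits as well as admissions. It is lay wording, not a classification rule, and section 5.6 separates hospitalizations from SAEs.
- The 24-hour clock starts when the investigator is notified. The only scheduled contact after discharge is the Day 30 call, so some readmissions will be learned of late whatever the definition says.

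What remains after these points is that nothing in the documents makes a heart failure or kidney readmission, as such, an SAE. Nor does anything say that such admissions are deliberately exempt.

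**Conclusion.** The concern holds in a limited form. The third criterion in 7.0 does not fit the collection window in 7.2. A new post-discharge admission as such, most clearly for heart failure or kidney failure, meets none of the five listed criteria. Unless it qualifies by another route, it is not required to be graded, assessed for causality or sent to the sponsor within 24 hours of notification. The loss is in classification, assessment and expedited sponsor reporting, not in data capture.

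The size is the text result: none of the five criteria names a new admission, and two of the six named admission reasons have only time-limited entries in 7.2. The documents give no readmission rate and no share that would qualify by another route, so they support no count of affected events.

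The effect on the halt rule is conditional. It concerns only readmissions judged unexpected, and 7.1 judges that against package inserts that are not part of these documents. It cannot be said that the halt would have been reached. The conclusion rests on reading prolongation in its ordinary sense, as excluding a fresh admission after discharge.

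**What to change.** In 7.0, extend the third criterion to new inpatient hospitalization or prolongation of an existing one, keeping the exceptions for elective and protocol-required stays. In 7.2 and Appendix C, state that non-elective admissions reported at the Day 30 call are entered on the SAE form. The qualifier is needed because the script asks about admission to any hospital, which would otherwise bring in elective stays. The time limits in the 7.2 list can stay as they are, since the amended criterion covers later admissions.

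If the intention is that disease-related readmissions after the treatment period are not SAEs, the protocol should say so and give the reason. That also removes the ambiguity.

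The cost is one phrase in 7.0, a sentence each in 7.2 and Appendix C, and a few more SAE forms with their grading, causality assessment and sponsor notices. The change does not bring forward the date on which a readmission becomes known. It settles what must happen once it is.

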7.1 Assessment of Causality

A medically-qualified investigator must assess the relationship of any SAE to the use of study drug, based on available information, using the following guidelines:

Possibly Related - There is a reasonable possibility that the adverse event may have been caused by the study drug. The temporal relationship of the adverse event to study drug administration makes a causal relationship possible, and other drugs, therapeutic interventions or underlying conditions do not provide sufficient explanation for the observed event.

Not Possibly Related- It is unlikely that the event was caused by the study drug. The temporal relationship of the adverse event to the study drug administration makes causal relationship unlikely and other drugs, therapeutic interventions or underlying conditions provide a more likely explanation for the event.

Expectedness - The expectedness of an adverse event or suspected adverse reaction shall be determined according to the package insert for U.S. marketed furosemide and tolvaptan. Any AE that is not identified in nature, severity, or specificity in the current U.S. package insert is considered unexpected. Events described in the U.S. package insert as occurring with a class of drugs or as anticipated from the pharmacological properties of the drug, but not specifically mentioned as occurring with the particular drug under investigation are considered unexpected.

7.2 Reporting of SAE

All serious adverse events occurring from randomization through the 30 day follow-up period will be collected. The Site Investigator is responsible for monitoring the safety of patients enrolled into the study. The following adverse events are anticipated, disease related-events in patients with decompensated heart failure however they should still be reported on the Serious Adverse Event form in the REDCAP Database (some may require reporting as study endpoints):

- New Atrial Arrhythmia: A “new” diagnosis of atrial arrhythmia (includes atrial fibrillation, atrial flutter, ectopic atrial tachycardia) lasting > 30 seconds OR any atrial arrhythmia which causes hemodynamic instability (MAP < 60 and requiring intervention)
- New Ventricular Arrhythmia: Ventricular tachycardia lasting longer than 30 seconds, or frequent non-sustained VT causing hemodynamic instability with MAP < 60 mmHg requiring intervention or > 1 intra-cardiac defibrillation or external cardiac defibrillation shock or ventricular fibrillation requiring defibrillation
- Hypotension: SBP < 85 for 2 repeated measurements within 30 minutes or lasting at least 30 minutes or symptomatic hypotension necessitating clinical intervention (defined as vasopressor support, intravenous fluid boluses, or initiation of inotropes)
- Myocardial infarction: a cardiac event including an elevation in troponin above baseline with or without ECG changes that is judged to be a myocardial infarction by the treating attending cardiologist
- Cardiac arrest: any ventricular arrhythmic or pulseless electrical event that requires immediate life-sustaining medical therapies
- Acute renal failure: A rise in serum creatinine of 1 mg/dl or more from the baseline serum creatinine in the 48 hour treatment period
- Acute renal failure requiring dialysis: an acute renal failure event that began during the 48 hour study period and necessitates new hemodialysis during the hospitalization

- Worsening heart failure: the need for rescue therapy (additional open label loop diuretic, spironolactone doses >75mg/day, eplerenone > 75mg/day, non-study thiazides (at a dose of metolazone 2.5mg or greater equivalence), systemic acetazolamide (for diuretic indication), triamterene, amiloride, ultrafiltration, hemodialysis, or mechanical circulatory or respiratory support) in the 48 hour treatment period
- Death
- Metabolic SAE (during 48 hour treatment period):
 - Severe Hypokalemia: Serum potassium value < 3.0mEq/L
 - Severe Hyponatremia: Serum sodium value < 130mEq/L and a decrease of 5mEq/L or more from enrollment serum sodium
 - Overcorrection of serum sodium: increase in serum sodium from baseline by ≥ 12 mEq/L in 24 hours, increase in >8mEq/L in 12 hours, or receipt of intravenous fluids because of symptoms of overcorrection of serum sodium regardless of the numerical rise
 - Hyperkalemia: serum potassium value > 5.5mEq/L
 - Gout: acute gout attack requiring treatment with an anti-inflammatory agent

All serious adverse events must be recorded in the Serious Adverse Event Record of the patient's REDCAP database. All serious adverse events should be monitored until stabilization or resolution.

Reporting to Local IRB. Investigators are also responsible for promptly reporting unexpected adverse events (serious and non serious) to their reviewing IRB in accordance with local requirements. The Vanderbilt investigational site will report DSM reports to the Vanderbilt IRB annually at the time of continuing review at a minimum. If 5 unexpected SAEs occur, the trial will be temporarily halted and the Vanderbilt IRB will be informed. After review, the study will resume if the IRB approves continuation with or without alterations in the study protocol.

Reporting to the Industry Sponsor

The investigator will notify the Sponsor within 24 hours of being notified of any SAE. The investigator will also notify the Sponsor of any pregnancy during the study period within 3 days of being notified. For all non-serious adverse events, the investigator will notify the Sponsor of all events as a line item list at the end of the study.

7.3 Study Termination

The study may be terminated based on review of serious adverse events and unexpected events. If 5 unexpected SAEs occur this will trigger a temporary halt to the study until additional review of these events is conducted by the PI and IRB.

8.0 Study Withdrawal/Discontinuation

A patient may withdraw at the study at anytime. The patient will inform the site investigator of their desire to withdraw. All study-based therapy will stop at this point, and the attending cardiologist will perform any further care. All study data collected to that time point will be included in the analysis. The withdrawal reason will be documented.

The site investigator will withdraw patients requiring therapy for overcorrection of serum sodium who experience any neurologic symptoms or who do not respond to intravenous D5W therapy within 6 hours. All patients will be followed per the study protocol through Day 30.

